Genetic counselors at St. Luke's Health System volunteered to participate in this study and contacted the AI about their interest in participating and hosting the study. The counselors at Medstar Washington Hospital Center were contacted by the AI after initial IRB approval of this protocol in order to increase recruitment by adding an additional site.

At the onset of data collection, counselors will complete a written consent. After each appointment with a study participant, genetic counselors will complete a short client empowerment survey. After the client study is complete, genetic counselors will be given a survey about their opinions about and experience with the self-affirmation intervention. Questions will include information on their experiences and opinions about the SA. Counselors at St. Luke's Health System will each be given a \$1400 gift card at the completion of the latter questionnaire. The counselors at Medstar see fewer potential participants so their compensation will be \$200. We expect to have approximately 16 patient participants from Medstar and 54 from St. Luke's Health System. In addition, the counselors at MedStar will be involved with recruitment over a shorter period of time and will not have to expend the effort expended by the St. Luke's counselors to work through logistics prior to the study's approval

**Figure 3:** *Participants participation in protocol*

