### **Counselor after visit survey (Appendix E)**

The counselor after visit survey consists of a counselor version of the Genetic Counseling Outcome Scale (GCOS-24). This scale was modified from the original GCOS-24 for use by counselors and parallels the client version. This measure consists of 24 likert scale questions that assess counselor's perceptions of the client's empowerment. It should take 3-5 minutes for the counselors to complete after each session.

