## **7.0 Description of study statistical considerations and/or analytic plan:**

*Aims have been copied here for ease of interpretation.*

Aim 1: To assess the preliminary impact of a novel SA intervention on outcomes that may be targeted in future studies, by assessing differences in the following between a SA intervention and unaffirmed standard SA intervention control group of HBOC genetic counseling clients:

- a. Intentions to talk with family, test uptake
- b. Empowerment, decision self-efficacy
- c. HBOC knowledge

The primary goal of analysis of aim 1 is to identify which outcomes would be most appropriate for follow up studies and the necessary sample size for adequate statistical power.

For decision efficacy, the scores on the Decision Self-Efficacy Scale (See section 2 of client survey, Appendix D) will be compared between groups using linear regression controlling for education, race, anxiety score, and effectiveness of intervention (based on last question on intervention Appendix C). Intention to talk with family, genetic testing uptake, and information seeking will be measured similarly using linear regression.

Client empowerment will be analyzed by using the GCOS-24 a 24-item likert scale completed by clients and parallel scale by genetic counselors (See section 3 of client survey of appendix D and appendix F). Both scales will be compared between groups using linear regression controlling for education, race, anxiety score, and effectiveness of intervention (based on last question on survey). Discrepancies between counselor and client surveys will be analyzed using dyadic analyses. For this analysis, we will assess the correlation between paired client and genetic counselor GCOS-24 for the compete survey and for the individual questions.

HBOC knowledge will be analyzed between groups using linear regression testing the knowledge scale (See section 4 of client survey, Appendix D) and controlling for education, race, anxiety score, and effectiveness of intervention.

Effect sizes and standard deviations for each outcome will be identified, and an estimated sample size for a fully powered study will be estimated based on power calculations.

Aim 2: To describe genetic counselors' (GCs) and clients' response to a novel, client-based SA intervention, including perceived impact, barriers, and facilitators to implementing such an intervention on a wider scale

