9.1 Therapeutic interventions *N/A*

9.2 Diagnostic interventions *N/A*

9.3 Radiation *N/A*

9.4 Sedation *N/A*

9.5 Risks to family relationships and other psychosocial or economic harms *N/A*

## 10.0 Description of how privacy and confidentiality of medical information/biological specimens will be maximized

Code words will be used to coordinate assembly of study documents and identifiable client information will not be connected with study documents. For initial surveys to be matched with post-session surveys for later analysis, clients will choose a code word compiled by asking: What is the first street that you lived on? What was your first pet's name? (e.g. OakMondo). This code word will be put on all documents relating to a given participant. The client will tell the counselor the code word during the appointment in order to label the counselors' post-visit survey, but no record of the code word in association with the client's name will be created. Cancer is a common condition and we do not expect clients to be identifiable through their diagnosis. Code words will be destroyed at completion of the study.

Genetic counselor surveys will not include identifying information for the counselor or which after-visit survey was conducted by each counselor. After-visit genetic counselor surveys will include the client code-word that will aid in confirming that surveys are being completed by counselors.

10.1 Description of any clinical/demographic information that will be included.

For clients, demographic information will be collected including: education, age, sex, race, and clinic site. No demographic information will be collected for counselors.

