10.2 How might this information make specific individuals or families identifiable?

Since an indication for HBOC genetic counseling is common it is unlikely that individuals will be identifiable from this information.

10.3 If research data will be coded, how will access to the "key" for the code be limited? Include description of security measures (e.g., password-protected database, other). List names or positions of persons with access to the "key" for the code.

The client will generate the code word based off the prompt "first street you grew up on + first pets name." There will not be a key to link the code word with the clients. The code word is designed to be easy for clients to remember. If the study materials do not have consistent code words than the AI will attempt to match surveys based on one of the two prompted words. If this cannot be accomplished with reasonable certainty that documents are from the same client, then the data will not be included in analysis. Counselors will know the code word to attach it to the counselor post-visit survey but will not keep a record of the code word associated with identifying client information.

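### The planned client-counselor discrepancy analysis on the GCOS-24 is a correlation of unnamed type, which in its usual forms cannot show a systematic gap in level between counselors and clients

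*Combined protocol and SAP*

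**What the plan says.** The client empowerment paragraph of Section 7.0 (Aim 1) names its target: "Discrepancies between counselor and client surveys will be analyzed using dyadic analyses". The next sentence gives the method: "we will assess the correlation between paired client and genetic counselor GCOS-24 for the compete survey and for the individual questions". It does not say whether the coefficient is Pearson, rank or intraclass. No paired difference, limits of agreement, concordance coefficient, agreement ICC or kappa appears anywhere in the document.

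Three other statements bear on the point:

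- Section 7.0 also plans an arm comparison of the client scale and of the counselor scale: "Both scales will be compared between groups using linear regression controlling for education, race, anxiety score, and effectiveness of intervention". Each regression compares arms within one scale, not counselor with client.
- For all Aim 1 outcomes, Section 7.0 adds: "Effect sizes and standard deviations for each outcome will be identified". It does not promise the two raters' means.
- Section 5.6 says of the counselor form: "This scale was modified from the original GCOS-24 for use by counselors and parallels the client version".

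**The concern.** A discrepancy between two raters of the same client has two parts: how far the gap varies from client to client, and whether one rater sits systematically above or below the other. The usual correlations speak to the first part only. Counselors could rate empowerment well above what their clients report, item after item, and the correlations could still be high. A reader who sees a high value under a heading of discrepancies may conclude that they are small.

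What is at stake is limited. A feasibility study that asks counselors for a 24-item form after every visit would leave unreported the simplest finding those forms can give: whether counselors over- or under-estimate client empowerment on average.

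**Working it through.** The plan states no figure for this analysis, so there is none to reproduce. The check is of how the statistic behaves.

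**Inputs.** From the document: at most 70 client-counselor pairs (Section 6.1), expected as 54 from St. Luke's and 16 from Medstar (Section 5.0). Pairs may be lost: where code words cannot be matched with reasonable certainty, Section 10.3 says "then the data will not be included in analysis". Assumed, because the document gives none: equal SDs for the two raters, the correlation r, and the gap d in SD units.

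**Step 1: response to an offset.** Adding a constant to one rater leaves that rater's deviations from the mean and rank order unchanged, so Pearson and rank coefficients do not move. Lin's concordance does. With equal SDs it is 2r/(2 + d²):

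| Gap d (SD) | Pearson, r = 0.8 | Concordance | Pearson, r = 0.5 | Concordance |
|---|---|---|---|---|
| 0 | 0.80 | 1.6/2 = 0.80 | 0.50 | 1/2 = 0.50 |
| 0.5 | 0.80 | 1.6/2.25 = 0.71 | 0.50 | 1/2.25 = 0.44 |
| 1 | 0.80 | 1.6/3 = 0.53 | 0.50 | 1/3 = 0.33 |

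**Step 2: numerical check.** In 70 simulated pairs scaled to Pearson 0.60 with equal SDs, offsets of 0, 0.25, 0.5, 1 and 2 SD left Pearson at 0.600, Spearman at 0.563, Kendall at 0.401 and the consistency ICC at 0.600. The absolute-agreement ICC fell through 0.60, 0.59, 0.54, 0.40 and 0.20.

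**Step 3: items.** Integer scores of 1 to 5 were shifted by 0, 1 or 2 points inside an assumed 1 to 7 range. Pearson stayed at 0.502 and Spearman at 0.480, while concordance went from 0.48 to 0.33 to 0.16. The invariance is exact only away from the scale ends: when larger shifts were clipped at 7, Pearson became 0.509 or 0.410.

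**Step 4: what the plan already yields.** If Pearson r and the two SDs come from the same complete pairs, the variance of the paired difference is s₁² + s₂² − 2·r·s₁·s₂. That fixes the width of the limits of agreement and, with the number of pairs, the width of the CI for the mean gap. Only the centre, the mean gap itself, is missing.

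**Step 5: precision if the mean gap is added.** With equal SDs of 1, the SD of the difference is √(2(1 − r)), and the 95% half-width is t × SD/√n, with pairs treated as independent.

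| | r = 0.8 | r = 0.5 | r = 0.3 |
|---|---|---|---|
| SD of difference | 0.632 | 1.000 | 1.183 |
| Limits of agreement, mean ± 1.96 SD | ±1.24 | ±1.96 | ±2.32 |
| Half-width, 70 pairs (t = 1.995) | 0.15 | 0.24 | 0.28 |
| Half-width, 50 pairs, assumed loss (t = 2.010) | 0.18 | 0.28 | 0.34 |
| Half-width, St. Luke's, 54 pairs (t = 2.006) | 0.17 | 0.27 | 0.32 |
| Half-width, Medstar, 16 pairs (t = 2.131) | 0.34 | 0.53 | 0.63 |

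**The case against.** The strongest reply is that correlation is a reasonable choice here. The counselor form was modified and records the counselor's perception of the client. Nothing in the document shows that the two forms share a zero, so part of any offset may be wording. A low correlation, overall or on an item, is itself evidence of discrepancy. The plan attaches no threshold or conclusion to the coefficient, and the analysis is descriptive and outside the listed specific aims.

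Much of this stands, and it rules out some stronger readings:

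- A reader might infer that the planned statistic misses discrepancies altogether. It does not: Step 4 shows that r with the planned SDs carries their spread. Only level is lost.
- A reader might infer that the study will wrongly report agreement. The plan sets no rule for reading the correlation, so this is a risk of misreading and not a planned misstatement.
- A reader might infer that counselor leniency cannot be examined at all, because Section 10.0 says: "Genetic counselor surveys will not include identifying information for the counselor or which after-visit survey was conducted by each counselor". But Section 10.1 records clinic site for clients, and Section 6.1 places two counselors at each site, so leniency is partly visible by site.
- A reader might want the gap compared between arms. Nothing in the stated target requires this, and it goes beyond the defect.

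The wording caveat does not rescue correlation as the only measure. The plan itself calls the forms parallel, and a caveat on how to interpret an offset is no reason to leave the offset unreported. Nor does the broad label of dyadic analysis, since the following sentence narrows it to correlation. An absolute-agreement ICC would respond to an offset, but the plan does not say that one is meant.

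**Conclusion.** The concern holds in a limited form. If the coefficient is Pearson, rank or a consistency ICC, the stated method reflects ordering and spread but cannot show a systematic difference in level between counselors and clients. That follows from the definition of the coefficients. The size is illustrative only, because r, the gap and equal SDs are assumed: at r = 0.8, a 1 SD gap leaves the correlation at 0.80 while concordance drops from 0.80 to 0.53.

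The change is worth making if convenient, but it is not essential. It leaves the arm regressions and the sample-size estimate untouched.

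**What to change.** In Section 7.0:

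1. Name the correlation coefficient and keep it as the measure of association.
2. Add the paired difference, counselor minus client total: its mean with 95% CI, and limits of agreement. An absolute-agreement ICC is optional.
3. Give the 24 item mean differences descriptively.
4. Report the number of matched pairs, and show results overall and by clinic site. The Medstar figure will be imprecise with about 16 pairs.
5. State two limitations. An offset may partly reflect the modified counselor wording. Individual counselors are not identified, so leniency can be examined only by site, and the interval applies to these four counselors and not to counselors in general.

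The cost is a few lines of text and a little extra analysis. The parallel forms, code-word matching and clinic site are already planned, so no form changes and the confidentiality commitment stands. The downside is that an offset, if found, cannot be attributed to one cause.

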### **Client post-intervention survey (Appendix D)**

Client surveys will consist of questions on each category of outcome (information seeking, test uptake, empowerment, intention to talk with family, decision self-efficacy, and HBOC knowledge) as well as response to and acceptance of the SA measure. The survey will be offered online and in person. It should take less than 15 min for participants to complete. At the end the hard copy post-intervention there will be a page for clients to enter their mailing address to receive the gift card, this page will be immediately separated from the other study materials by the scheduling coordinator. The online survey will have a separate link for clients to enter their mailing address.

**Decision self-efficacy.** To measure decision self-efficacy in decisions regarding genetic testing for HBOC and we will use the Decision Self-Efficacy Scale (O'Connor, 1995). This scale focuses on the decision process and interactions with the medical professional so it gives insight into both decisional efficacy and clients' engagement with the clinician.

**Test uptake.** For this section we will ask two questions to test uptake; "Did your counselor offer you genetic testing in your counseling appointment?" (yes/no) and "If yes, do you plan to have genetic testing?" (yes/no).

**Intention to talk with family.** Intention to talk with family will be measured using two questions. The first is a question asking clients to select the categorical description of the family group they are most likely to share information with from a list of options, such as "I plan to talk to only a few people who are closest to me." The second question will state "How likely are you to share results with the relatives you selected?" will be rated on a 1-7 likert scale labeled "extremely likely to extremely unlikely."

**Empowerment.** Empowerment will be assessed using the valid and reliable Genetic Counseling Outcomes Survey (GCOS-24) (McAllister et al, 2011). The GCOS-24 is a 24 item instrument that was designed to measure positive outcomes of genetic counseling. Empowerment was conceptualized to include decisional control, cognitive control, behavioral control, emotional regulation, and hope. The scale has seven dimensions, which exist under a single higher order construct.

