## **6.0 Description of study population**

#### 6.1 Estimated number of participants, enrollment ceiling, and anticipated enrollment by year.

The client participants will be female patients being seen at the high-risk breast and ovarian cancer clinic at St. Luke's Health System and Medstar Washington Hospital Center, for their initial appointment for genetic counseling for HBOC. Participant selection will be indiscriminant of if they have cancer or if they have already had genetic testing through another provider. Participants must be at least 18 years of age. For a fully powered study of the effect of self-affirmation on genetic counseling outcomes, we estimate that we would need 296 participants to identify a small to medium effect (Cohen's  $d = 0.35$ ) with beta being 0.85 and alpha being 0.05. This Cohen's  $d$  is based on other SA interventions in the education and emerging medical literature. For this feasibility study we seek to recruit 70 client participants and 4 genetic counselor participants. We chose this number for several reasons. The genetic counselors at St. Luke's Health System see about 40 new patients a month. Over the 4 months of data collection there will be 180 appointments. We believe that getting 70 of these clients to consent is an achievable estimation. Additionally, feasibility studies typically range from 30-50 participants to estimate attrition and confidence intervals. The enrolment ceiling is 180 participants. Genetic counselor participants two genetic counselors at the St. Luke's health system HBOC clinic. Participants will be enrolled by February of 2018. To this point, we have been recruiting about 8 patients a month instead of expected 17 through St. Luke's Health System. To our knowledge, this is because the counselors are seeing more colorectal and other cancer patients than expected instead of HBOC patients and we have been able to reach less patients for consent. About half decline to be contacted and 1/3 cannot be reached by the AI for consent. For this reason, we are adding the Medstar Washington Hospital Center site and extending the recruitment window. Genetic counselor participants are two genetic counselors employed in the HBOC genetic counseling clinic at St. Luke's Hospital and two genetic counselors who see HBOC patients at Medstar Washington Hospital Center.

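### The paired client–counselor GCOS-24 step sets out to analyse discrepancies but specifies only pooled correlations, which miss systematic over- or under-rating and cannot show whether self-affirmation changes the discrepancy.

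*Combined protocol and SAP*

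**What the plan says.** Aim 1 in section 7.0 concerns differences between the SA and control groups, and its main purpose is to "identify which outcomes would be most appropriate for follow up studies and the necessary sample size for adequate statistical power". For empowerment the section plans two things.

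- A between-arm comparison of the client GCOS-24 and of the counselor version, each on its own: "Both scales will be compared between groups using linear regression controlling for education, race, anxiety score, and effectiveness of intervention".
- A paired step: "Discrepancies between counselor and client surveys will be analyzed using dyadic analyses". The next sentence defines it: "we will assess the correlation between paired client and genetic counselor GCOS-24 for the compete survey and for the individual questions".

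For the paired step the plan gives no arm term, by-arm estimate, difference score, confidence interval or reporting rule.

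Other relevant text:

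- Section 5.6 (Counselor after visit survey) says of the counselor form: "This measure consists of 24 likert scale questions that assess counselor's perceptions of the client's empowerment". It is described as parallel to the client version.
- Section 6.1 sets the target: "For this feasibility study we seek to recruit 70 client participants and 4 genetic counselor participants". Section 5.0 splits the clients 35 and 35.
- Clients may skip questions (section 6.5), and documents that cannot be matched by code word are left out of the analysis (section 10.3).
- Section 3.0 (Feasibility study) does not expect significant results and wants effect sizes and confidence intervals.

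**The concern.** The stated purpose and the stated method do not match, in two ways.

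First, a discrepancy is a difference between two scores for the same client, whereas a correlation describes whether the two scores rise and fall together. Counselors could credit every client with far more empowerment than she reports, and the correlation could still be high.

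Second, the step sits under a between-arm aim meant to screen outcomes for a larger trial, yet it pools the arms. Counselors complete a 24-item form after every participating visit. As planned, the pairing of those forms with the clients' forms gives no estimate of whether SA brings the two views closer together or moves them apart.

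A smaller matter is the correlation for each of the 24 items. Without intervals or a descriptive label, items with high and low correlations could be read as real differences in agreement when sampling error may explain much of the gap.

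**Working it through.** **The plan's own figure.** No sample size or precision is stated for the paired step. The only sample-size figure is 296 for a future full study (section 6.1: d = 0.35, alpha 0.05, and 0.85, which is written as beta but works as power). The two-sided normal formula gives 2(1.960 + 1.036)²/0.35² = 146.6, so 147 per arm or 294 in total; the t-test version gives 296. The figure reproduces and is not at issue.

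**Step 1: a constant shift is invisible to r.** With client score C, counselor score G and constant k, cov(C, G − k) = cov(C, G) and SD(G − k) = SD(G), so r is unchanged. In 70 simulated pairs, subtracting 2 from every counselor score left r at 0.577, while the mean of C − G rises by exactly 2.

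**Step 2: pooling hides an arm difference.** If means and SDs are equal in both arms, true correlations of 0.50 and 0.10 pool to (0.50 + 0.10)/2 = 0.30. So do 0.30 and 0.30. The planned figure cannot tell these cases apart.

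**Step 3: precision of one correlation.** The Fisher interval is tanh(atanh r ± 1.96/√(n − 3)).

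- n = 70 (target), r = 0.30: 0.3095 ± 1.96/√67 = 0.3095 ± 0.2395, giving 0.07 to 0.50.
- n = 50 (assumed loss; the documents give no rate), r = 0.30: 0.02 to 0.53.
- n = 70, r = 0.50: 0.30 to 0.66.

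**Step 4: how far item differences could be sampling error.** The sampling variance of r is about (1 − r²)²/(n − 1). At r = 0.30 and n = 70 this is 0.91²/69 = 0.0120, an SD of 0.11. Let τ be the SD of the true item correlations, which the documents do not give. The share of the observed spread due to sampling is 0.0120/(0.0120 + τ²):

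| assumed τ | share |
|---|---|
| 0.05 | 83% |
| 0.10 | 55% |
| 0.15 | 35% |
| 0.20 | 23% |

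Sampling error is the larger part only if τ is below about 0.11. At the extreme where all 24 items share a true r of 0.30, simulated item correlations still run on average from about 0.07 to 0.50.

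**Step 5: what an arm contrast would deliver.** Let D = C − G on the total score, in units of its SD, with 35 per arm.

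- Detectable at 80% power, two-sided 0.05: (1.960 + 0.842)√(2/35) = 0.67.
- Approximate 95% half-width when the true d is near zero: 1.96√(2/35) = 0.47.
- With 25 per arm (assumed loss): 2.802√(2/25) = 0.79 and 1.96√(2/25) = 0.55.

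Comparing correlations by arm instead would be weak: the SE of the Fisher z difference is √(2/32) = 0.25, and power for 0.30 against 0.50 is 16%.

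**The case against.** The strongest reply is that client–counselor agreement is not an Aim 1 outcome. The aim lists intentions to talk with family, test uptake, empowerment, decision self-efficacy and knowledge, and nowhere does the plan suggest that SA changes agreement. That is correct, so a reader who infers that the plan promises an SA effect on agreement and fails to deliver it goes too far. What remains is the mismatch between announcing discrepancies and computing correlations, and a paired step that does not serve the aim it sits under.

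Nor is arm missing from the GCOS-24 analysis. Both scales are compared by arm. If the two regressions use the same pairs and covariates, the arm coefficient for C − G equals the client coefficient minus the counselor coefficient, so the signed contrast is already implied as a point estimate. Its interval is not, because that needs the within-dyad covariance, and nothing planned yields the absolute difference.

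A reader might also infer that the item-level discrepancies will be mostly chance. The documents do not support this. They give no item correlations, and step 4 spans 23% to 83%. Simulations with every item equally in agreement make all the spread chance by construction. Even there, the chance that at least one item correlation is negative runs from about 0% to 96% across the assumed loadings and latent correlations.

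Three further limits on the criticism stand. The total-score correlation is planned alongside the items. Seventy is a target, with an enrolment ceiling of 180, although skipped items and unmatched code words could also leave fewer pairs. The plan sets no item-level test, and descriptive item results are ordinary in a feasibility study. The protocol says of the GCOS-24 that "The scale has seven dimensions, which exist under a single higher order construct", but replacing the items with seven dimension scores would be a preference, not a correction.

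**Conclusion.** The point holds and is minor. As written, the paired step cannot detect a systematic gap between client and counselor ratings and cannot show whether SA alters that gap. Both statements follow from the definition of a pooled correlation and need no numerical assumption.

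The caution on items is one of precision: at 70 pairs an item correlation of 0.30 is compatible with anything from 0.07 to 0.50. Differences between items may therefore reflect sampling error, to a degree that depends on the unknown true spread.

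The figures treat pairs as independent. They come from four counselors, and sections 6.5 and 10.0 say surveys will not be linked to individual counselors. Clustering by counselor therefore cannot be modelled, and the intervals may be too narrow. The difference score also assumes that the two forms share a response range and scoring direction, as the word parallel suggests; the appendices are not in the text reviewed.

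**What to change.** In section 7.0, under client empowerment:

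1. Keep the total-score correlation and report it with a 95% CI.
2. Add the client-minus-counselor total difference for each dyad, signed and absolute, with mean and SD by arm. Regress each on arm and report an effect size with a 95% CI, as an estimate and not a test.
3. Report the item-level correlations as descriptive only, with CIs.
4. State that at about 35 per arm the contrast is imprecise (about d = 0.67 detectable at 80% power; approximate for the absolute difference, which is skewed).

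While editing, reconcile the appendix reference: section 7.0 points to Appendix F for the counselor scale, and section 5.6 places it in Appendix E.

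The cost is a few sentences of plan text and a few lines of analysis on data already being collected. The downside is one more imprecise estimate in a small study, which the stated interval makes plain.
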